CAB and POPS-PAT stakeholders is on reducing childhood obesity across the population in a region that experiences disparities across educational, economic, and racial sub-groups. However, we do plan on conducting exploratory subgroup analysis of the heterogeneity treatment effects (HTE) that will inform hypothesis generation that can be tested in future pragmatic trials for assessing the robustness of the interventions in achieving public health benefit across subgroups. The POPS-CAB and POPS-PAT identified three individual attributes that may modify program effect based on our NIH-R24 planning grant results: race, gender and parent health literacy status at baseline. Interactions (two-way and three-way) among those factors and time and group indicators will be added to the above multi-level mixed effect models to be tested. Even though we are not powered for the HTE analysis, all standard sub-group analysis estimation and reporting protocols will be followed. As part of the exploratory HTE analysis plan, we will also estimate the HTE method proposed by Imai and Ratkovic⁹⁹ which addresses HTE as a variable selection problem and the method is shown to be appropriate for exploring HTE.

5. What is your plan for secondary variable analysis?

Secondary Aim #1: Reach/representativeness will be analyzed following the recommendations of Glasgow et al.⁹⁰ Participation rate will be calculated as total n enrolled/ total n of eligible participants exposed to recruitment. To improve the comparison of representativeness we will, using a similar multi-level mixed effect logit models as presented above, create a summary effect size (ES) for differential characteristics by using the median ES across the comparisons of demographic, health, and behavioral information of participants versus those declining participation. (Using the median rather than the mean will minimize the influence of outliers). The median ES will then be subtracted from the participation rate to provide a summary measure of reach. Summary descriptive statistics reporting rates and cost of completion of in-person and IVR follow-ups will be computed for implementation indicators. Fidelity will be assessed as proportion of the intervention that is delivered as intended across intervention components based on IVR data and delivery agent fidelity checklists. These data will be reported descriptively and in concert with cost data. A concurrent mixed methods design will be used to collect quantitative and qualitative data collected on implementation and triangulated for interpretation.¹⁰⁰ Finally, summary RE-AIM metrics will be calculated as detail by Glasgow et al.

Secondary Aim #2: Using mixed methods,¹⁰⁰ quantitative capacity dimensions will be analyzed using repeated measures ANOVA, accounting for differences between community and academic members. Interviews will be transcribed. A minimum of two members will code meaning units from each transcript using NVIVO and a hybrid inductive-deductive analysis approach to identify emergent themes related to capacity dimension.¹⁰¹⁻¹⁰³

Secondary Aim #3: Similar multi-level mixed effect models as in primary aim 1 will be used. The dependent variables will be family eating behaviors, child and parents' physical activity levels and parent weight at each time point. The coefficient θ will

IRB-HSR # 19748: A randomized-controlled trial to compare the reach, effectiveness and maintenance of two family-based childhood obesity treatment programs in a medically underserved region

capture the potential differences by treatment condition. For those discrete outcomes, appropriate link functions and distribution assumptions will be used in the modeling.

Secondary Aim #4: At each time point, those who drop out of the study will be compared on key demographic variables with those retained in order to understand the mechanism of participation both by group mean tests and by selection bias testing in selection models. Different adherence/attendance to classes and phone calls will be summarized following similar usage metrics by Donkin including a composite measure of exposure (i.e., exposure=intensity x frequency x duration).¹⁰⁴ Both ANOVA and selection models that handle and test potent nonrandom dose exposure resulted from natural choices will be used to analyze dose responses.

6. Have you been working with a statistician in designing this protocol?

Yes

IF YES, what is their name?

[name], Associate Professor at Virginia Tech

7. Will data from multiple sites be combined during analysis?

No

Information from Outside Institution

1. List the names of outside institutions that will be supplying data and/or specimens for this study.

Contact and eligibility information of children are being provided by SOVAH Pediatrics and Piedmont Access to Health Services (PATHS) by review of medical records (see file: Tracking eligible children), but no other data is being provided by SOVAH Pediatrics or PATHS.

The University of Nebraska Medical Center (UNMC) is responsible for developing and managing the web-based platform for the collection of self-reported behavioral and quality of life data from parents and children. However, UNMC is not screening or enrolling participants at their site, there only a single Danville site for this study.

2. Describe the type of information you will receive from each site.

SOVAH Pediatrics and PATHS will provide the research team with contact information and basic demographics for eligible children who are between the ages of 5-12 years and >85th %ile BMI: name, address, phone, birthdate, gender, race/ethnicity, type of insurance. The web-based platform developed by UNMC will include: eating and physical activity habits, health status, quality of life, and perceptions of the home environment.

3. Does the outside institution have an IRB?

Yes, University of Nebraska Medical Center has an IRB. De-identified data will be sent to UNMC under contract.

IRB-HSR # 19748: A randomized-controlled trial to compare the reach, effectiveness and maintenance of two family-based childhood obesity treatment programs in a medically underserved region

A letter of support is provided from SOVAH Pediatrics and PATHS.

Biomedical Research

1. What will be done in this protocol?

Parent/Child Dyads.

Families have an equal chance of being randomly assigned to any one of the two programs. They cannot choose to which program they are assigned.

GROUP 1: iChoose

The iChoose program will last for 12 months. During the first six months families will be asked to:

- Attend 12 small group education sessions every other week. The health classes are for both the parent and child and will include information on nutrition and exercise.
- Attend one hour family exercise sessions two times a week (total of 48 sessions, 12 of which are part of the small group education sessions)
- Complete 12 automated telephone calls to provide support to help families reach your eating and physical activity goals.
- The child will also get 12 mailed newsletters to help them meet their program goals.

During the last six months of the program parents will continue to get support calls every other week (a total of 12 more calls) and your child will get 12 more newsletters.

See additional study procedures listed in #2 below.

GROUP 2: Family Connections

The Family Connections program will last for 6 months. During this time parents will be asked to:

- Attend 2 education sessions that are one week apart. The health classes are for parents/guardians only and will include information on parental role modeling regarding healthy nutrition and exercise behaviors.
- Complete 10 automated telephone calls to provide support families reach your eating and physical activity goals. There will be 2-3 calls per month during months 1-3 and then 1 call per month during months 4-6.

Community Advisory Board and Parent Advisory Team. Meeting procedures provided above in the study design section. (NOTE: the meetings are not part of the research procedures, only the mixed-methods evaluation, as described below. The participation in meetings is a contractual arrangement for advisory board members).

2. List the procedures, in bullet form, that will be done for RESEARCH PURPOSES as stipulated in this protocol.

IRB-HSR # 19748: A randomized-controlled trial to compare the reach, effectiveness and maintenance of two family-based childhood obesity treatment programs in a medically underserved region

Interventions: The iChoose and Family Connections interventions are described above and in the study design section.

ALL of the following procedures are being done for research purpose.

SEE ATTACHMENTS:

1. Parent Survey
2. Child Survey
3. Summative evaluation_iChoose parents
4. Summative evaluation_iChoose child
5. Summative evaluation_Family Connection parents
6. Summative evaluation_Family Connections child
7. CAB_PCORI_Capacity Eval QUANT survey
8. CAB_PCORI_Capacity Eval Qualitative survey
9. PAT_PCORI_Capacity Eval QUANT survey
10. PAT_PCORI_Capacity Eval Qualitative survey

Parent/Child Dyads.

The following health assessment will occur at baseline, 6-month and 12-month assessments among both the children ages 8-12 and parents.

- Height
- Weight
- Blood pressure
- Waist circumference
- Self-reported questionnaires (Parent Survey and Child Survey), pertaining to
 - Eating habits
 - Physical activity habits (via computer)
 - Quality of life/Health status (via computer)
 - Health literacy (via pencil/paper)
 - Home environment (parents only)(via computer)

At the 3-moth assessment: only height and weight are collected for parent and children. Parents will also complete a brief interview (PCORI 3 month assessment) examining program satisfaction, adherence, and retention.

At 6- and 12-month assessments: Post-program evaluation, quantitative ratings and qualitative interview.

For children ages 5-7, the Child Survey will be abbreviated to those measures validated for this age range. As such, only anthropometric data (height, weight, blood pressure, and waist circumference) and the Quality of Life questionnaire (as described on the 'Child Survey') will be collected. Assistance with computer administered surveys will be

IRB-HSR # 19748: A randomized-controlled trial to compare the reach, effectiveness and maintenance of two family-based childhood obesity treatment programs in a medically underserved region

provided for this age range by the research staff. Children 5-7 will also receive the same qualitative interviews at 6 and 12 months as the 8-12 year olds.

NOTE: Due to COVID-19 social distancing regulations an amendment to this protocol expands questionnaire data collection for parents and children (8 years-12 years) to mailed paper and pencil modality. This modality will only apply to Cohort 3 12 month follow-up data. Assistance with reading the survey over the phone will be offered to those who request this service. Researchers will explore the data for response differences at this time point to help determine any undue impacts from this change.

Community Advisory Board

- Mixed-methods evaluation, quantitative survey and qualitative interview questions, pertaining to: communication, trust, decision making procedures, conflict resolution, group roles, problem assessment, collective efficacy, leadership, accomplishments and impact, participation and influence, community power, resources, sustainability, and overall satisfaction.
- This evaluation will occur annually, or at three time points, during the study.

Parent Advisory Team

- Mixed-methods evaluation, quantitative survey and qualitative interview questions, pertaining to: communication, problem assessment, collective efficacy, leadership, participation and influence, community power, overall satisfaction, and influence. Qualitative will also include questions pertaining to PAT's role to assist in family recruitment activities and to assist in family adherence by providing a program 'safety net'.
- This evaluation will occur annually, or at three time points, during the study.

3. Do you confirm that, except for blood draws through a peripheral site, that all invasive procedures will be performed by a licensed health care provider under the supervision of an MD?

There are no invasive procedures in this protocol.

4. Will you be using data/specimens in this study that were collected previously, with the use of a research consent form, from another research study?

No

5. Will any of the procedures listed in item # 2 have the potential to identify an incidental finding? This includes ALL procedures, assessments and evaluations that are being done for RESEARCH PURPOSES that may or may not be considered investigational.

It is possible that a subject's blood pressure reading would be out of the range of normal

X The examination(s) utilize(s) the same techniques, equipment, etc., that would be used if the subject were to have the examination(s) performed for clinical care. **There exists the potential for the discovery of clinically significant incidental findings.**

- The PI takes full responsibility for the identification of incidental findings:
- The PI will inform the subjects verbally of all incidental findings that are of clinical significance or are of questionable significance.
- A follow-up letter describing the finding should be provided to the subject with instructions to either show the letter to their PC or if the subject has no PCP, the subject should be instructed to make an appointment at UVa or at the Free Clinic.

6. Do any of the procedures listed above, under question # 2, utilize any imaging procedures for RESEARCH PURPOSES?

No

7. Will you be using viable embryos?

No

8. Will you be using embryonic stem cells?

No

9. If this protocol involves study treatment, explain how a subject will be transitioned from study treatment when they have completed their participation in the study.

Once the family-based childhood obesity treatment interventions have ended, the parent/child dyad participants will resume their usual medical care, at their own cost.

10. Will your study involve measures used to screen or assess for depression and/or suicidality for research purposes? No

11. Where will the study procedures be done?

Check One:

UVA medical center facilities (In patient or outpatient)
 UVa , but not medical center facilities: LIST specific location

Answer/Response:

X Other LIST specific location Answer/Response:

Danville site: These procedures will occur in community centers owned by our Parks and Recreation partners in Danville, VA.

Chatham site: These procedures will occur in the Pittsylvania Parks and Recreation Community Center in Chatham, VA.

IRB-HSR # 19748: A randomized-controlled trial to compare the reach, effectiveness and maintenance of two family-based childhood obesity treatment programs in a medically underserved region

At both sites efforts will be taken to make sure participants are comfortable during the health screenings and measurements will be taken in a private area.

12. If the study involves medical risk and study procedures will be done outside of the UVa Medical Center what is your plan to protect the subjects in case of a medical emergency?

Note: Exercise sessions are no greater in intensity than might be encountered in everyday life, during recreational activities offered by Danville Parks and Recreation.

Check all applicable options:

- MD, RN, onsite during procedures
- Individual trained in CPR on site during procedures
- AED and Individual trained to use it onsite
- Call 911
- Other : Describe Answer/Response:

13. Are any aspects of the study kept secret from the participants? No

14. Is any deception used in the study? No

Taping/Photography

1. Will participants be recorded on audiotape?

Parent/Child Dyads: No

Community Advisory Board: yes, for research purposes

Parent Advisory Team: yes, for research purposes

1a. What steps will be taken to protect the privacy of the subjects?

All recordings will be assigned an anonymous id number, and names will be removed from transcriptions. All names will be removed from transcriptions. Audio files will be deleted once transcription is complete.

1b. What data will be captured from the audiotapes?

Qualitative interviews from the Community Advisory Board and Parent Advisory Team will be collected on audio tape.

1c. When will data from the tapes be transcribed?

Data from the audiotapes will be transcribed within 6 months of being collected.

1d. When will the audiotapes be destroyed?

IRB-HSR # 19748: A randomized-controlled trial to compare the reach, effectiveness and maintenance of two family-based childhood obesity treatment programs in a medically underserved region

The audiotapes will be destroyed after the transcriptions have occurred and been checked for accuracy.

2. Will participants be photographed or recorded on videotape?

Photographs may be used for promotion purposes for this protocol and only from all participants (parents, children, and Community Advisory Board and Parent Advisory Team members) who sign a photograph release form. Promotional activities will include various print and electronic media. Also, photographs may be used in the newsletters as a part of the iChoose+ program. Videotapes will not be used in this study.

2a. Will their faces be shown?

Yes

2b. What steps will be taken to protect the privacy of the subjects?

Photographs will only be used among participants who have signed a photo release form. This is not a requirement for participation in any aspect of this study. Names will not be attached to photographs unless otherwise approved by the participants.

2c. What data will be captured from the photo or videotape that could not be obtained in other ways?

The photographs are not for data or analysis purposes. Photographs will be used in IRB-approved ads, and/or conference presentations when subjects agree.

2d. How is this data critical to this research?

The photographs are not for data or analysis purposes.

2e. When will data from the tapes be transcribed?

N/A

2f. When will the tapes be destroyed?

There are no videotapes.

2g. Will participants be photographed, recorded or videotaped without their knowledge?

No

3. If a subject withdraws from the study how will you withdraw them from the audiotape, videotape or photograph?

If a subject withdraws they will not participate in any additional qualitative interviews involved with the Community Advisory Board and Parent Advisory Team capacity evaluation. Their previous recorded information, prior to when they withdraw, will still be used. If a participant withdraws who previously had a photo release form, we will not use their photographs for any additional promotional purposes effective the date of study withdrawal.

Data and Safety Monitoring Plan

Adverse events will only be collected or recorded if a causal relationship to the study intervention is suspected. If any adverse event is considered serious and unexpected, the event must be reported to the IRB-HSR within 7 days from the time the study team receives knowledge of the event.

1. Definitions

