The Dan River Region (DRR): Obesity, Disparities, & Community Action. Obesity prevalence is a public health concern that is a national priority.¹⁻³ The outcomes of sustained obesity include diabetes, cardiovascular disease, and some forms of cancer.¹⁻⁴ Increased rates of obesity in children are related to 'adult' diseases such as type 2 diabetes and hypertension presenting during childhood.⁴ Of particular concern is the persistence of disparities related to obesity for children from low income, minority, and geographically dispersed groups in the population.^{5,6} The DRR, located in south central Virginia and north central North Carolina, characterizes these disparities. The DRR is a

confluence of social determinants of health that includes low socio-economic status, a high proportion of racial minorities, and small regional cities that lack resources to address obesity. The DRR includes the city of Danville, Pittsylvania, Henry and Caswell Counties and is a federally designated, medically underserved area burdened with educational, economic, and health disparities.⁷⁻¹² Regional unemployment rates are nearly double the state and national averages,¹³ and 27% of residents are black, 16.5% live below the Federal Poverty Level, and only 9% have obtained a bachelor's degree.^{8,9} Furthermore, rates of low literacy levels exceed state averages by nearly 20%.⁷ Although childhood obesity data are limited, one local school district showed 17% of 1st graders were overweight and 19% were obese.¹⁴ By 5th grade, this cohort increased prevalence to 19% overweight and 36% obese. This rate of obesity is 3 times higher than state averages (~11% of VA youth are obese). Prevalence of adult chronic diseases such as obesity (~35%) and type 2 diabetes (27-33%), are significantly higher than state averages (25% obesity; 19.5% diabetes) and further illustrate serious regional health concerns.^{7,12,15}

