IRB-HSR # 19748: A randomized-controlled trial to compare the reach, effectiveness and maintenance of two family-based childhood obesity treatment programs in a medically underserved region

Advisors (PHA). Since the POPS-PAT members expressed commitment to providing a social-support safety-net for *iChoose* families, are from the target population, share common demographics and cultural traits, and have already experienced a FBCO—members of the POPS-PAT have agreed to expand their roles into a formal PHA model. In combination with the proposed PHA training, *we anticipate these characteristics will promote connectedness to, and trust with targeted families and improve adherence and outcomes.*

Hypothesis to be Tested

The primary study hypotheses are:

- Effectiveness-- children in both conditions will reduce BMI-z scores significantly, when compared to baseline at 3, 6 and 12 months, but *iChoose+* reductions will be significantly larger than Family Connections,
- reach—the sample will be representative of the eligible regional population on demographic and behavioral factors
- implementation—the intervention components will be delivered with high fidelity in both conditions, but costs will be lower for Family Connections
- maintenance—a sustainability action plan will be completed to include strategies for continued delivery of *iChoose+* and/or Family Connections (outcome dependent)
- parent weight, parent/child behaviors, & tertiary outcomes that follow the same patterns as BMI z-scores
- community capacity for implementing and sustaining a locally relevant FBCO treatment and maintenance program will remain high over time

Study Design: Biomedical

1. Will controls be used?

Parent/Child Dyads: yes

Community Advisory Board: no

Parent Advisory Team: no

► IF YES, explain the kind of controls to be used.

This is comparative effectiveness trial, below is a description of the two programs:

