- In addition, up to 496 subjects will be enrolled with waiver of documentation of consent. This group will include subjects who signed written consent for the main study, and subjects who completed the telephone survey but did not enroll in the main study.

5. Provide an estimated time line for the study.

For parent/child dyads in the comparative effectiveness trial:

- Cohort 1= intervention 6/2017-5/2018 (w/ 3-, 6-, & 12 months f/u)
- Cohort 2= intervention 4/2018-3/2019 (w/ 3-, 6-, & 12 months f/u)
- Cohort 3= intervention 2/2019-1/2020 (w/ 3-, 6-, & 12 months f/u)

- Year 1: 66% enrolled, 33% completed
- Year 2: 100% enrolled, 66% completed

IRB-HSR # 19748: A randomized-controlled trial to compare the reach, effectiveness and maintenance of two family-based childhood obesity treatment programs in a medically underserved region

- Year 3: 100% completed

For both the Community Advisory Board and Parent Advisory Team, 100% enrolled in Year 1; mixed-methods evaluation at end of each study year

Inclusion/Exclusion Criteria

1. List the criteria for inclusion

Cohorts 1-2:

Parent/child dyads in the comparative effectiveness trial, families are eligible to participate if they

- have a child between -12 years old with a BMI percentile that is 85% or greater for their age and gender
- live in the Dan River Region
- are English speaking
- parents/caregivers ≥ 18 years of age

Community Advisory Board members were identified and named when the PCORI application was submitted:

- Representatives from organizations in the Dan River Region who have a child-focused organizational mission, invited as a stakeholder
- ≥ 18 years of age
- Willing and able to provide informed consent

Parent Advisory Team members:

- Parent who previously participated in a childhood obesity program and/or are the parent of a child ages 8-12 years of age
- ≥ 18 years of age
- live in the Dan River Region

Cohort 3:

Parent/child dyads in the comparative effectiveness trial, families are eligible to participate if they

- have a child between 5-12 years old with a BMI percentile that is 85% or greater for their age and gender
- live in the Dan River Region
- are English speaking
- parents/caregivers ≥ 18 years of age

IRB-HSR # 19748: A randomized-controlled trial to compare the reach, effectiveness and maintenance of two family-based childhood obesity treatment programs in a medically underserved region

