Community Advisory Board members were identified and named when the PCORI application was submitted:

- Representatives from organizations in the Dan River Region who have a child-focused organizational mission, invited as a stakeholder
- ≥18 years of age
- Willing and able to provide informed consent

Parent Advisory Team members:

- Parent who previously participated in a childhood obesity program and/or are the parent of a child ages 5-12 years of age
- ≥18 years of age
- live in the Dan River Region

2. List the criteria for exclusion

Parent/child dyads:

- children with a major cognitive impairment based on medical record review or contraindications for physical activity
- families that are already participating in a childhood obesity treatment program

Community Advisory Board: none

Parent Advisory Team:

- Cannot simultaneously be enrolled in the comparative effectiveness trial and serve on the Parent Advisory Team

3. List any restrictions on use of other drugs or treatments.

Parent/child dyads

- families that are already participating in a childhood obesity treatment program will be excluded

Community Advisory Board and Parent Advisory Team: NA

Statistical Considerations

1. Is stratification/randomization involved?

Yes

► IF YES, describe the stratification/ randomization scheme.

We will use simple randomization, at the parent-child dyad level. Randomization is not blinded. The researchers will have access to the randomization scheme.

► IF YES, who will generate the randomization scheme?

Sponsor
 UVa Statistician. Answer/Response:

UVa Investigational Drug Service (IDS)
 X Other: [name], statistician from Virginia Tech

2. What are the statistical considerations for the protocol?

- The primary end-point is 6-month reduction in BMI z-score.
- We calculated a standardized effect size relative to the differences in BMI z-scores and standard deviations *related to 6-month BMI z-score reduction* for *Family Connections* (0.07) and *Bright Bodies* as a target for the *iChoose+* condition (BMI z-score reduction = 0.16).

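### A significant fall from baseline within each arm is listed as primary effectiveness, but with no untreated arm neither a fall nor its absence can be attributed to a programme

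*Combined protocol and SAP*

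**What the plan says.** Hypothesis to be Tested lists the primary study hypotheses. The one labelled Effectiveness has two parts:

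- Within-arm: "children in both conditions will reduce BMI-z scores significantly, when compared to baseline at 3, 6 and 12 months".
- Between-arm: iChoose+ "reductions will be significantly larger than Family Connections".

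A later bullet expects parent weight, parent and child behaviours and tertiary outcomes to behave in the same way as BMI z-score. The maintenance bullet says that "a sustainability action plan will be completed to include strategies for continued delivery of" iChoose+ and/or Family Connections, depending on outcome.

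There is no untreated arm. Under Study Design, the question on controls is answered with "This is comparative effectiveness trial, below is a description of the two programs", and Biomedical Research, item 1 says "Families have an equal chance of being randomly assigned to any one of the two programs". Entry is on the outcome variable: for cohort 3, families must "have a child between 5-12 years old with a BMI percentile that is 85% or greater for their age and gender", and the same percentile applies in cohorts 1 and 2.

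The rest of the plan is comparative. The abstract's primary aim is relative effectiveness. Statistical Considerations, item 2 says "The primary end-point is 6-month reduction in BMI z-score"; item 3 sizes the trial on the difference between programmes; item 4 takes the treatment effect from θ, the arm-by-time coefficient. No section limits how a within-arm fall may be read, mentions regression to the mean, or names an external comparator for it.

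**The concern.** Testing each arm against baseline treats zero as the no-treatment course. Two forces make that doubtful, and they oppose each other. Children selected for a high BMI z-score tend to be measured lower later. Against this, Background, section A reports a local school cohort going from 17% overweight and 19% obese in 1st grade upward: "By 5th grade, this cohort increased prevalence to 19% overweight and 36% obese". Randomisation removes both forces from the comparison between arms and from nothing else.

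What is at stake is the conclusion when the arms do not differ. If both fall significantly, the hypothesis as worded lets the report say that both programmes were effective. If one arm stays flat, it lets the report say that this programme failed, although holding BMI z-score level could be a benefit where untreated children rise. The design supports neither statement.

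**Working it through.** **The plan's own figure.** No calculation is given for the within-arm clause. The only sample size is for the between-arm difference: standardised effect 0.73, with 58 or 64 per group for 80% or 85% power. At two-sided 0.05, 2(1.960 + 0.842)²/0.73² gives 30 and 2(1.960 + 1.036)²/0.73² gives 34. The stated 58 and 64 are therefore not reproduced; they match an effect of about 0.52 to 0.53. That is a separate matter. It is used here only to bracket the SD of 6-month change. The planned reductions are 0.16 and 0.07, a difference of 0.09, so the SD is 0.09/0.73 = 0.123 or 0.09/0.53 = 0.17.

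**Inputs.** Entry cut at the 85th percentile, z = 1.036; 64 completers per arm. Assumptions: normal z-scores with SD 1; correlation r between baseline and 6 months; the qualifying value is also the baseline; no programme effect. Three population means μ are used:

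- μ = 0, the reference population.
- μ = 1.645 − 0.878 = 0.767, matching 19% obese (taken as above the 95th percentile).
- μ = 1.645 − 0.358 = 1.286, matching 36% obese.

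**Formulas.** With k = 1.036 − μ and λ = φ(k)/(1 − Φ(k)):

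- Regression to the mean = (1 − r)λ, where λ = 1.554, 0.977 and 0.646 for the three means.
- SD of change = √[(1 − r)²V + 1 − r²], where V is the variance of z above the cut (0.19, 0.31, 0.42). For example, r = 0.95 and μ = 0 give √(0.0005 + 0.0975) = 0.313.
- The chance of a significant fall in one arm is the upper tail of the non-central t with 63 df and non-centrality 8 × fall/SD, beyond the two-sided 5% critical value. For both arms it is the square.

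**Results, no drift.** Each cell gives spurious fall in z; chance in one arm; chance in both.

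| r (SD of change) | μ = 0 | μ = 0.767 | μ = 1.286 |
|---|---|---|---|
| 0.95 (0.31) | 0.078; 50%; 25% | 0.049; 23%; 5% | 0.032; 13%; 1.6% |
| 0.98 (0.20) | 0.031; 23%; 5% | 0.020; 12%; 1.4% | 0.013; 7%; 0.5% |
| 0.986 (0.17) | 0.022; 18%; 3% | 0.014; 9%; 0.9% | 0.009; 6%; 0.4% |
| 0.992 (0.126) | 0.012; 12%; 1.4% | 0.008; 7%; 0.5% | 0.005; 5%; 0.3% |

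With no regression to the mean the chances are 2.5% and 0.025² = 0.06%. A simulation of 1,500 trials per setting at μ = 0 with zero effect agrees: both arms fell significantly in 5%, 11% and 23% of trials at r = 0.98, 0.97 and 0.95. The between-arm test stayed at 4.5%, 4.7% and 5.2%.

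**Drift the other way.** Taking 1st to 5th grade as four years, or eight half-years, the rise in obesity implies (1.286 − 0.767)/8 = 0.065 z per 6 months. Overweight plus obesity, 36% to 55%, implies (0.358 + 0.126)/8 = 0.061. At r = 0.95 the net untreated change is then:

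- μ = 0: 0.078 − 0.065 = a fall of 0.013.
- μ = 0.767: 0.049 − 0.065 = a rise of 0.016.
- μ = 1.286: 0.032 − 0.065 = a rise of 0.033.

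At r = 0.98 the drift exceeds regression to the mean in all three populations.

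**The case against.** The strongest reply is that confirmatory planning is already between-arm. The aim, sample size and θ all concern the contrast, and no separate within-arm test is specified. This stands, and it confines the defect to one clause. It does not remove the clause, which sits among the primary hypotheses with no statement of how it may be read.

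Three stronger readings are tempting, and the documents support none of them.

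- *A spurious fall is likely.* A reader might pair a fall of 0.04 with the SD of 0.123 to 0.17 and find it significant in 73% to 46% of trials per arm. The inputs do not match. A fall that large needs r near 0.95 (or about 0.974 at μ = 0), and with SD 1, r = 0.95 makes the SD of change about 0.31, where a fall of 0.04 is significant in about 17%. An SD of 0.123 to 0.17 means r of about 0.992 to 0.986 and regression to the mean of only 0.005 to 0.022.
- *Selection makes values drift down overall.* The school trend can cancel or reverse this, in which case testing against zero is conservative. Baseline may also not be the qualifying value. Families found by chart review qualify on a chart BMI and are measured again at enrolment, which would shrink the effect by an unknown amount. For those answering advertisements, height and weight are taken before consent, and Appendix: Recruitment does not say whether that value is also the baseline.
- *The within-arm result will decide which programme is sustained.* Risk/Benefit Analysis, item 1 ties local decisions to differences between the programmes together with sustainability data, and cost and reach are already outcomes.

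A last objection concerns timing. The version is dated 04/22/2020, after the scheduled cohort 3 intervention window (2/2019 to 1/2020), so deleting part of a prespecified hypothesis is not a neutral edit. This is fair, and it favours demoting the clause openly over removing it.

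**Conclusion.** The point holds for the within-arm clause only. A fall from baseline in either arm, or its absence, does not identify a programme effect, because the no-treatment course is unknown in size and direction. Regression to the mean alone could be about 0.005 to 0.08 z, against the 0.07 planned for Family Connections. It would produce a significant fall in about 5 to 50% of trials per arm and 0.3 to 25% for both arms, with the top values only at μ = 0 and r = 0.95. In the two populations matched to local obesity prevalence, the both-arm figure is about 5% or less.

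These figures rest on assumed normality, SD 1, r, no drift and the qualifying value as baseline. They describe the 6-month time point alone; requiring falls at 3 and 12 months as well could only lower them. The drift of about 0.06 z comes from a whole school cohort and may not apply to children above the cut. The conclusion does not depend on any one of these values. The randomised comparison remains valid.

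**What to change.** In Hypothesis to be Tested, state that effectiveness is judged by the randomised between-arm contrast in 6-month BMI z-score (θ in Statistical Considerations, item 4). Keep the within-arm clause visible but label it descriptive: change from baseline in each arm with a 95% confidence interval, not attributed to the programmes, and not enough by itself to conclude that both programmes work. Apply the same rule to the parent, behavioural and tertiary outcomes tied to the same pattern. It would help to state whether the eligibility measurement also serves as baseline.

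No change to data collection, sample size or model follows. Because the change comes late, and interim analyses are planned after each cohort's 6-month assessment, date it and record what outcome data had been seen. It only narrows what may be claimed. The cost is giving up a within-arm effectiveness claim that the design cannot support.
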